Appendix 5. Translation of the Danish summary of product characteristics

SUMMARY OF PRODUCT CHARACTERISTICS

for

Pantoprazol "Actavis", powder for solution for injection

1. NAME OF THE MEDICINAL PRODUCT

Pantoprazol "Actavis" 40 mg powder for solution for injection

2. QUALITATIVE AND QUANTITATIVE COMPOSITION

Each vial contains 40 mg of pantoprazole (as sodium sesquihydrate)

Excipients with known effect:

Each vial contains 5.0 mg of sodium citrate dihydrate and sodium hydroxide q.s.

This medicinal product contains less than 1 mmol sodium (23 mg) per vial, i.e. is essentially "sodium free".

For the full list of excipients, see section 6.1

3. PHARMACEUTICAL FORM

Powder for solution for injection.

White or almost white, uniform porous cake.

For the solution reconstituted with 10 ml of 0.9% NaCl solution the pH is approximately 10 and the osmolality is approximately 382 mOsm/Kg

For the solution reconstituted with a further 100 ml of 0.9% NaCl solution or 5% glucose solution the pH is approximately 9 and 8.5, respectively

4. CLINICAL PARTICULARS

4.1 Therapeutic indications

- Reflux oesophagitis
- Gastric and duodenal ulcer
- Zollinger – Ellison Syndrome and other pathological hypersecretory conditions.

4.2 Posology and method of administration

This medicine should be administered by a healthcare professional and under appropriate medical supervision.

The intravenous administration of pantoprazole is recommended only if oral application is not appropriate. Data are available on intravenous use for up to 7 days. Therefore as soon as oral therapy is possible, treatment with pantoprazole i.v. should be discontinued and 40 mg pantoprazole p.o. should be administered instead.

Posology

Gastric and duodenal ulcer, reflux oesophagitis

The recommended intravenous dose is one vial of pantoprazole (40 mg) per day.

Zollinger-Ellison Syndrome and other pathological hypersecretory conditions

For the long-term management of Zollinger-Ellison Syndrome and other pathological hypersecretory conditions patients should start their treatment with a daily dose of 80 mg of pantoprazole i.v. Thereafter, the dosage can be titrated up or down as needed using measurements of gastric acid secretion to guide. With doses above 80 mg daily, the dose should be divided and given twice daily. A temporary increase of the dosage above 160 mg pantoprazole is possible but should not be applied longer than required for adequate acid control.

In case a rapid acid control is required, a starting dose of 2 x 80 mg of pantoprazole i.v. is sufficient to manage a decrease of acid output into the target range (<10 mEq/h) within one hour in the majority of patients.

Special populations

Paediatric population

The experience in children is limited. Therefore, pantoprazole i.v. is not recommended for use in patients below 18 years of age until further data become available.

Hepatic impairment:

A daily dose of 20 mg pantoprazole (half a vial of 40 mg pantoprazole) should not be exceeded in patients with severe liver impairment (see section 4.4).

Renal impairment:

No dose adjustment is necessary in patients with impaired renal function.

Elderly

No dose adjustment is necessary in elderly patients.

Method of administration

A ready-to-use solution is prepared in 10 ml of sodium chloride 9 mg/ml (0.9%) solution for injection. For instructions for preparation see section 6.6. The prepared solution may be administered directly or may be administered after mixing it with 100 ml of 9 mg/ml (0.9%) sodium chloride injection, or 50 mg/ml glucose (5%) solution for injection.

After preparation the solution must be used within 12 hours (see section 6.3).

The medicinal product should be administered intravenously over 2 – 15 minutes.

4.3 Contraindications

Hypersensitivity to the active substance, substituted benzimidazoles, or to any of the excipients listed in section 6.1.

4.4 Special warnings and precautions for use

In presence of alarm symptoms

In the presence of any alarm symptom (e.g. significant unintentional weight loss, recurrent vomiting, dysphagia, haematemesis, anaemia or melaena) and when gastric ulcer is suspected or present, malignancy should be excluded, as treatment with pantoprazole may alleviate symptoms and delay diagnosis.

Further investigation is to be considered if symptoms persist despite adequate treatment.

Hepatic impairment

In patients with severe liver impairment, the liver enzymes should be monitored during therapy. In the case of a rise in the liver enzymes, the treatment should be discontinued (see section 4.2).

Co-administration with atazanavir

Co-administration of atazanavir with proton pump inhibitors is not recommended (see section 4.5). If the combination of atazanavir with a proton pump inhibitor is judged unavoidable, close clinical monitoring (e.g. virus load) is recommended in combination with an increase in the dose of atazanavir to 400 mg with 100 mg of ritonavir. A pantoprazole dose of 20 mg per day should not be exceeded.

Gastrointestinal infections caused by bacteria

Pantoprazole, like all proton pump inhibitors (PPIs), might be expected to increase the counts of bacteria normally present in the upper gastrointestinal tract. Treatment with pantoprazole may lead to a slightly increased risk of gastrointestinal infections caused by bacteria (e.g. *Salmonella* and *Campylobacter* and *C.difficile*).

Sodium

This medicinal product contains less than 1 mmol (23 mg) sodium per dose, i.e. essentially “sodium-free”.

4.5 Interaction with other medicinal products and other forms of interaction

Effect of pantoprazole on the absorption of other medicinal products

Because of profound and long lasting inhibition of gastric acid secretion, pantoprazole may reduce the absorption of drugs with a gastric pH dependant bioavailability, e.g. some azole antifungals such as ketoconazole, itraconazole, posaconazole and other medicines such as erlotinib.

HIV medications (atazanavir)

Co-administration of atazanavir and other HIV medications whose absorption is pH-dependent with proton pump inhibitors might result in a substantial reduction in the bioavailability of these HIV medications and might impact the efficacy of these medicines. Therefore, the co-administration of proton pump inhibitors with atazanavir is not recommended (see section 4.4).

Coumarin anticoagulants (phenprocoumon or warfarin)

Although no interaction during concomitant administration of phenprocoumon or warfarin has been observed in clinical pharmacokinetic studies, a few isolated cases of changes in International Normalised Ratio (INR) have been reported during concomitant treatment in the post-marketing period. Therefore, in patients treated with coumarin anticoagulants (e.g. phenprocoumon or warfarin), monitoring of prothrombin time/INR is recommended after initiation, termination or during irregular use of pantoprazole.

Other interactions studies

Pantoprazole is extensively metabolised in the liver via the cytochrome P450 enzyme system. The main metabolic pathway is demethylation by CYP2C19 and other metabolic pathways include oxidation by CYP3A4.

Interaction studies with drugs also metabolised with these pathways, like carbamazepine, diazepam, glibenclamide, nifedipine and an oral contraceptive containing levonorgestrel and ethinyl oestradiol did not reveal clinically significant interactions.

Results from a range of interaction studies demonstrate that pantoprazole does not effect the metabolism of active substances metabolised by CYP1A2 (such as caffeine, theophylline), CYP2C9 (such as piroxicam, diclofenac, naproxen), CYP2D6 (such as metoprolol), CYP2E1 (such as ethanol) or does not interfere with p-glycoprotein related absorption of digoxin.

Methotrexate

Concomitant use of high dose methotrexate (e.g. 300 mg) and proton-pump inhibitors has been reported to increase methotrexate levels in some patients. Therefore in settings where high-dose methotrexate is used, for example cancer and psoriasis, a temporary withdrawal of pantoprazole may need to be considered.

There were no interactions with concomitantly administered antacids.

Interaction studies have also been performed administering pantoprazole concomitantly with the respective antibiotics (clarithromycin, metronidazole, amoxicillin). No clinically relevant interactions were found.

4.6 Fertility, pregnancy and lactation

Pregnancy

There are no adequate data from the use of pantoprazole in pregnant women. Studies in animals have shown reproductive toxicity (see section 5.3). The potential risk for humans is unknown. Pantoprazole should not be used during pregnancy unless clearly necessary.

Breast-feeding

Animal studies have shown excretion of pantoprazole in breast milk. Excretion into human milk has been reported. Therefore a decision on whether to continue/discontinue breast-feeding or to continue/discontinue therapy with pantoprazole should be made taking into account the benefit of breast-feeding to the child and the benefit of pantoprazole therapy to women.

4.7 Effects on ability to drive and use machines

Adverse drug reactions such as dizziness and visual disturbances may occur (see section 4.8). If affected, patients should not drive or operate machines.

4.8 Undesirable effects

Approximately 5% of patients can be expected to experience adverse drug reactions (ADRs). The most commonly reported ADRs are diarrhoea and headache, both occurring in approximately 1% of patients.

The table below lists adverse reactions reported with pantoprazole, ranked under the following frequency classification:

Very common ($\geq 1/10$); common ($\geq 1/100$ to $< 1/10$); uncommon ($\geq 1/1,000$ to $< 1/100$); rare ($< 1/10,000$ to $< 1/1,000$), very rare ($1/10,000$) not known (cannot be estimated from the available data). For all adverse reactions reported from post-marketing experience, it is not possible to apply any Adverse Reaction frequency and therefore they are mentioned with a "not known" frequency.

Within each frequency grouping, adverse reactions are presented in order of decreasing seriousness.

Table 1. Adverse reactions with pantoprazole in clinical trials and post-marketing experience

Frequency \ System organ class	Common	Uncommon	Rare	Very rare	Not known
Blood and lymphatic system disorders			Agranulocytosis	Thrombo-Cytopenia; Leukopenia; Pancytopenia	
Immune system disorders			Hypersensitivity (including anaphylactic reactions and anaphylactic shock)		
Metabolism and nutrition disorders			Hyperlipidaemia and lipid increases (triglycerides, cholesterol); Weight changes		Hyponatraemia Hypomagnesaemia; Hypocalcaemia in association with hypomagnesaemia; Hypokalaemia

Frequency System organ class	Common	Uncommon	Rare	Very rare	Not known
Psychiatric disorders		Sleep disorders	Depression (and all aggravations)	Disorientation (and all aggravations)	Hallucination: Confusion (especially in pre-disposed patients, as well as the aggravation of these symptoms in case of pre-existence)
Nervous system disorders		Headache; Dizziness	Taste disorders		Paraesthesia
Eye disorders			Disturbances in vision/blurred vision		
Gastrointestinal disorders		Diarrhoea; Nausea/ vomiting; Abdominal distension and bloating; Constipation; Dry mouth; Abdominal pain and discomfort.			
Hepatobiliary disorders		Liver enzymes increased (transaminases, γ -GT)	Bilirubin increased		Hepatocellular injury; Jaundice; Hepatocellular failure
Skin and sub-cutaneous tissue disorders		Rash/ exanthema/ eruption; Pruritus	Urticaria; Angioedema		Stevens-Johnson syndrome; Lyell syndrome; Erythema multiforme; Photo-sensitivity
Musculo-skeletal and connective tissue disorders			Arthralgia; Myalgia		Muscle spasm as a consequence of electrolyte disturbances
Renal and urinary disorders					Interstitial nephritis (with possible progression to renal failure)
Reproductive system and breast disorders			Gynaecomastia		
General disorders and administration site conditions	Injection site thrombophlebitis	Asthenia, fatigue and malaise	Body temperature increased; Oedema peripheral		

Reporting of suspected adverse reactions

Reporting suspected adverse reactions after authorisation of the medicinal product is important. It allows continued monitoring of the benefit/risk balance of the medicinal product. Healthcare professionals are asked to report any suspected adverse reactions.

4.9 Overdose

There are no known symptoms of overdose in man.

Systemic exposure with up to 240 mg administered intravenously over 2 minutes was well tolerated. As pantoprazole is extensively protein bound, it is not readily dialysable.

In case of overdose with clinical signs of intoxication, apart from symptomatic and supportive treatment, no specific therapeutic recommendations can be made.

5. PHARMACOLOGICAL PROPERTIES

5.1 Pharmacodynamic properties

Pharmacotherapeutic group: Proton pump inhibitors, ATC code: A02BC02.

Mechanism of action

Pantoprazole is a substituted benzimidazole which inhibits the secretion of hydrochloric acid in the stomach by specific blockade of the proton pumps of the parietal cells.

Pantoprazole is converted to its active form in the acidic environment in the parietal cells where it inhibits the H⁺/K⁺-ATPase enzyme i.e. the final stage in the production of hydrochloric acid in the stomach. The inhibition is dose-dependent and affects both basal and stimulated acid secretion. In most patients, freedom from symptoms is achieved within 2 weeks. As with other proton pump inhibitors and H₂ receptor inhibitors, treatment with pantoprazole reduces acidity in the stomach and thereby increases gastrin in proportion to the reduction in acidity. The increase in gastrin is reversible. Since pantoprazole binds to the enzyme distal to the cell receptor level, it can inhibit hydrochloric acid secretion independently of stimulation by other substances (acetylcholine, histamine, gastrin). The effect is the same whether the product is given orally or intravenously.

The fasting gastrin values increase under pantoprazole. On short-term use, in most cases they do not exceed the upper limit of normal. During long-term treatment, gastrin levels double in most cases. An excessive increase, however, occurs only in isolated cases. As a result, a mild to moderate increase in the number of specific endocrine (ECL) cells in the stomach is observed in a minority of cases during long-term treatment (simple to adenomatoid hyperplasia). However, according to the studies conducted so far, the formation of carcinoid precursors (atypical hyperplasia) or gastric carcinoids as were found in animal experiments (see section 5.3) have not been observed in humans.

An influence of a long term treatment with pantoprazole exceeding one year cannot be completely ruled out on endocrine parameters of the thyroid according to results in animal studies.

5.2 Pharmacokinetic properties

General Pharmacokinetics

Pharmacokinetics do not vary after single or repeated administration. In the dose range of 10 to 80 mg the plasma kinetics of pantoprazole are linear after both oral and intravenous administration.

Distribution

Pantoprazole's plasma protein binding is about 98%. Volume of distribution is about 0.15 l/kg.

Elimination

The substance is almost exclusively metabolised in the liver. The main metabolic pathway is demethylation by CYP2C19 with subsequent sulphate conjugation, other metabolic pathways include oxidation by CYP3A4. Terminal half-life is about 1 hour and clearance is about 0.1 l/h/kg. There were few cases of subjects with delayed elimination. Because of specific binding of pantoprazole to the proton pumps of the parietal cell the elimination half-life does not correlate with the much longer duration of action (inhibition of acid secretion).

Renal elimination represents the major route of excretion (about 80%) for the metabolites of pantoprazole; the rest are excreted in the faeces. The main metabolite in both the serum and urine is desmethylpantoprazole which is conjugated with sulphate. The half-life of the main metabolite (about 1.5 hours) is not much longer than that of pantoprazole.

Characteristics in patients/special groups of subjects:

Approximately 3% of the European population lack a functional CYP2C19 enzyme and are called poor metabolisers. In these individuals the metabolism of pantoprazole is probably mainly catalysed by CYP3A4. After a single dose administration of 40 mg pantoprazole, the mean area under the plasma concentration-time curve was approximately 6 times higher in poor metabolisers than in subjects having a functional CYP2C19 enzyme (extensive metabolisers). Mean peak plasma concentrations were increased by about 60%. These findings have no implications for the posology of pantoprazole.

No dose reduction is recommended when pantoprazole is administered to patients with impaired renal function (including dialysis patients). As with healthy subjects, pantoprazole's half-life is short. Only very small amounts of pantoprazole are dialysed. Although the main metabolite has a moderately delayed half-life (2-3 hours), excretion is still rapid and thus accumulation does not occur.

Although for patients with liver cirrhosis (classes A and B according to Child) the half-life values increased to between 7 and 9 hours and the AUC values increased by a factor of 5 to 7, the maximum serum concentration only increased slightly by a factor of 1.5 compared with healthy subjects.

A slight increase in AUC and C_{max} in elderly volunteers compared with younger counterparts is also not clinically relevant.

Paediatric population

Following administration of single intravenous doses of 0.8 or 1.6 mg/kg pantoprazole to children aged 2 – 16 years there was no significant association between pantoprazole clearance and age or weight. AUC and volume of distribution were in accordance with data from adults.

5.3 Preclinical safety data

Preclinical data reveal no special hazard to humans based on conventional studies of safety pharmacology, repeated dose toxicity and genotoxicity.

In the two-year carcinogenicity studies in rats neuroendocrine neoplasms were found. In addition, squamous cell papillomas were found in the forestomach of rats. The mechanism leading to the formation of gastric carcinoids by substituted benzimidazoles has been carefully investigated and allows the conclusion that it is a secondary reaction to the massively elevated serum gastrin levels occurring in the rat during chronic high-dose treatment. In the two-year rodent studies an increased number of liver tumours was observed in rats and in female mice and was interpreted as being due to pantoprazole's high metabolic rate in the liver.

A slight increase of neoplastic changes of the thyroid was observed in the group of rats receiving the highest dose (200 mg/kg). The occurrence of these neoplasms is associated with the pantoprazole-induced changes in the breakdown of thyroxine in the rat liver. As the therapeutic dose in man is low, no harmful effects on the thyroid glands are expected.

In animal reproduction studies, signs of slight fetotoxicity were observed at doses above 5 mg/kg. Investigations revealed no evidence of impaired fertility or teratogenic effects.

Penetration of the placenta was investigated in the rat and was found to increase with advanced gestation. As a result, concentration of pantoprazole in the foetus is increased shortly before birth.

6. PHARMACEUTICAL PARTICULARS

6.1 List of excipients

Mannitol

Sodium citrate dihydrate

Sodium hydroxide (for pH adjustment)

6.2 Incompatibilities

This medicinal product must not be mixed with other medicinal products except those mentioned in section 6.6.

6.3 Shelf life

As packaged for sale: 3 years

After reconstitution, or reconstitution and dilution, chemical and physical in-use stability has been demonstrated for 12 hours at 25°C. The reconstituted, or reconstituted and diluted medicinal product should not be refrigerated.

From a microbiological point of view, the product should be used immediately. If not used immediately, in-use storage times and conditions prior to use are the responsibility of the user.

6.4 Special precautions for storage

Do not store above 25°C. Keep the vial in the outer carton to protect from light.

For storage conditions of the reconstituted and diluted medicinal product see section 6.3.

6.5 Nature and contents of container

15 ml, type I, colourless glass vial, sealed with a grey chlorobutyl stopper and an aluminium flip-off cap, containing 40 mg pantoprazole powder for solution for injection.

Pack sizes: 1, 5, 10 and 20 vials

Not all pack sizes may be marketed.

6.6 Special precautions for disposal and other handling

A ready-to-use intravenous solution is prepared by injecting 10 ml of sodium chloride 9 mg/ml (0.9%) solution for injection into the vial containing the lyophilised powder. The reconstituted solution should be clear and colourless. This solution may be administered directly or may be administered after mixing it with 100 ml of sodium chloride 9 mg/ml (0.9%) solution for injection or glucose 50 mg/ml (5%) solution for injection. Glass or plastic containers should be used for dilution

Pantoprazol "Actavis" 40 mg powder for solution for injection should not be prepared or mixed with solvents other than those stated.

This medicine should be administered intravenously over 2- 15 minutes.

The content of the vial is for single use only. Any product that has remained in the container or the visual appearance of which has changed (e.g. if cloudiness or precipitation is observed) should be disposed of in accordance with local requirements.

Appendix 6. Adverse reactions not registered

Thrombocytopenia will not be registered as a serious adverse reaction (SAR) since it is a frequent condition among critically ill patients and is a part of the inclusion criteria (coagulopathy).

Increased plasma levels of bilirubin, (jaundice) and liver enzymes (hepatocellular injury) is not registered as they in themselves are not considered serious conditions. The potential serious consequence hepatic failure will be registered daily as a SAR.

Hyponatremia, hypokalaemia, hypomagnesaemia and hypocalcaemia will not be registered as electrolyte disturbances as they are frequent among ICU patients. These conditions are monitored and treated daily in all ICU patients. According to the summary of product characteristics, hypomagnesaemia will not be relevant until treatment for at least three months and in most cases one year.

Leukopenia will not be registered. Reduced white blood cell counts are frequent among ICU patients and can be associated with many different systemic or hematological disorders in critically ill patients.

Renal and urinary disorders will not be registered as they are not considered serious conditions in themselves, but the potential serious consequence will be reflected in the outcome measure days alive without use of renal replacement therapy.

The following possible adverse reactions will not be registered as SARs as they are not considered serious conditions:

Hyperlipidaemia, lipid increases, weight changes, taste disorders

Sleep disorders, depression, disorientation, hallucination, confusion, headache, dizziness

Paraesthesia, blurred vision

Nausea, vomiting, abdominal distension, constipation, dry mouth, abdominal pain and discomfort

Rash, exanthema, pruritus, erythema multiforme, photosensitivity, urticarial, hypersensitivity

Arthralgia, myalgia, asthenia, fatigue and malaise

Reproductive system, breast disorders, gynecomastia

Injection site thrombophlebitis

Body temperature increased

Oedema peripheral

Fracture of the hip, wrist or spine (treatment > 1 year)

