Appendix 1. Trial organisation

Appendix 2. Undesirable effects of pantoprazole

Approximately 5% of patients can be expected to experience adverse drug reactions. The most commonly reported adverse drug reactions are diarrhoea and headache, both occurring in approximately 1% of patients.

For all adverse reactions reported from post-marketing experience, it is not possible to apply any adverse reaction frequency and therefore they are mentioned with a “not known” frequency.

Within each frequency grouping, adverse reactions are presented in order of decreasing seriousness.

Adverse reactions with pantoprazole in clinical trials and post-marketing experience

Frequency	Common*	Uncommon*	Rare*	Very rare*	Not known
System Organ Class					
Blood and lymphatic system disorders			Agranulocytosis	Thrombocytopenia; Leukopenia Pancytopenia	
Immune system disorders			Hypersensitivity (including anaphylactic reactions and anaphylactic shock)		
Metabolism and nutrition disorders			Hyperlipidaemia as and lipid increases (triglycerides, cholesterol); Weight changes		Hyponatraemia Hypomagnesaemia (see section 4.4) Hypocalcaemia in association with hypomagnesemia; Hypokalaemia
Psychiatric disorders		Sleep disorders	Depression (and all aggravations)	Disorientation (and all aggravations)	Hallucination; Confusion (especially in pre-disposed patients, as well as the aggravation of these symptoms in case of pre-existence)

Nervous system disorders		Headache Dizziness	Taste disorders		Paraesthesia
Eye disorders			Disturbances in vision / blurred vision		
Gastrointestinal disorders		Diarrhoea; Nausea / vomiting; Abdominal distension and bloating; Constipation; Dry mouth; Abdominal pain and discomfort			
Hepatobiliary disorders		Liver enzymes increased (transaminases, γ -GT)	Bilirubin increased		Hepatocellular injury; Jaundice; Hepatocellular failure
Skin and subcutaneous tissue disorders		Rash / exanthema / eruption; Pruritus	Urticaria; Angioedema		Stevens-Johnson syndrome; Lyell syndrome; Erythema multiforme; Photosensitivity
Musculoskeletal and connective tissue disorders		Fracture of the hip, wrist or spine (see section 4.4)	Arthralgia; Myalgia		Muscle spasm as a consequence of electrolyte disturbances
Renal and urinary disorders					Interstitial nephritis (with possible progression to renal failure)
Reproductive system and breast disorders			Gynaecomastia		

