Agranulocytosis is defined as any new, acute and severe drop in granulocytes to $< 0.5 \times 10^9/l$ requiring active monitoring or treatment

Pancytopenia is defined as any new, severe drop in red blood cells, white blood cells and platelets requiring active monitoring or treatment

Acute hepatic failure is defined as severe and progressing hepatic failure as judged by the treating doctor or the investigator

Steven-Johnson syndrome and toxic epidermal necrolysis are defined as severe dermatological reactions with a skin biopsy confirming the diagnosis

Interstitial nephritis is defined as a nephritis affecting the interstitium of the kidneys surrounding the tubules with a kidney biopsy confirming the diagnosis

Angioedema (Quincke's oedema) is defined as a vascular reaction involving the deep dermis, subcutaneous or submucosal tissues, resulting in a characteristic localized oedema.

Adverse reactions not registered will be discussed in *appendix 6*.

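### Appendix 6 bars registration of renal and urinary disorders, although the only labelled reaction in that class, interstitial nephritis, is a registered SAR in Appendix 4

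*Combined protocol and SAP*

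**What the plan says.** Section 8.3 of the protocol divides pantoprazole reactions between two appendices: Appendix 4 defines the SARs that are registered, and Appendix 6 discusses the reactions that are not.

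- **Appendix 4**, in its list of SAR definitions: "Interstitial nephritis is defined as a nephritis affecting the interstitium of the kidneys surrounding the tubules with a kidney biopsy confirming the diagnosis".
- **Appendix 6**, on the kidney: "Renal and urinary disorders will not be registered as they are not considered serious conditions in themselves". It adds that "the potential serious consequence will be reflected in the outcome measure days alive without use of renal replacement therapy".
- **Appendix 6**, further down, introduces a list with "The following possible adverse reactions will not be registered as SARs as they are not considered serious conditions". One line of that list reads "Rash, exanthema, pruritus, erythema multiforme, photosensitivity, urticarial, hypersensitivity".

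The wording is the same in the original and the amended protocol. Amendments 1 and 2 concern Danish consent and Amendment 3 the monitoring committee charter, so none of them touches it.

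SARs are a secondary outcome in protocol section 7.2 (number of SARs) and in the SAP (secondary outcome 6, patients with at least one SAR). They are also compared between groups at interim analysis and reported yearly to the monitoring committee.

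**The concern.** A kidney biopsy showing interstitial nephritis, suspected to be due to trial drug, meets an Appendix 4 SAR definition and also falls in the class that Appendix 6 says is not to be registered. An investigator could omit it and still be following the protocol's text.

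The SAR field matters here because little else in the plan would identify the event. Section 8.3.1 says that serious adverse events are not recorded as an entity. Section 8.1 limits SUSARs to serious reactions that the product summary does not describe, and interstitial nephritis is described there. If the SAR field is left blank, the case could be missing from a safety outcome, from the interim safety comparison and from the notice to the coordinating investigator that a SAR entry triggers.

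**Working it through.** The plan gives no figure on this point, so the check is a comparison of texts.

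1. **What the excluded class contains.** The phrase that Appendix 6 uses is the name of a system organ class in Appendix 2 and in section 4.8 of the product summary (Appendix 5). In both tables the row has one entry, under frequency not known: "Interstitial nephritis (with possible progression to renal failure" (closing bracket omitted). Read against the protocol's own tables, the Appendix 6 sentence excludes exactly one labelled reaction.

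2. **What Appendix 4 does with that reaction.** It registers it as a SAR, subject to biopsy confirmation. The biopsy condition narrows the set of cases but does not remove the conflict, because Appendix 6 makes no exception for a biopsy-proven case.

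3. **Whether an exception is implied.** For the liver, Appendix 6 drops raised bilirubin and enzymes but says expressly that hepatic failure stays a daily-registered SAR. For the kidney it keeps no SAR and refers the serious consequence to a different outcome. A site comparing the two paragraphs could take the difference as intended.

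4. **Whether a precedence rule exists.** Section 8.3 cites both appendices and states none. Three pointers nevertheless lead to Appendix 4: section 8.3 for registered SARs, the outcome in section 7.2, and the daily SAR item in section 9.2.2. A site using these would register the case.

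5. **Whether renal replacement therapy would show the event.** It would not identify it, for three reasons.
   - Nephritis managed without renal replacement therapy leaves those days unchanged. Plasma creatinine is listed in section 9.2.2 only among the baseline variables.
   - Renal replacement therapy is recorded daily as yes or no, without a cause, and it is itself a qualifying risk factor for entry.
   - It is one of three components of the life-support outcome, alongside ventilation and circulatory support.

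6. **Hypersensitivity.** The Appendix 6 line quoted above includes this word without qualification. The corresponding entry in Appendix 2 is "Hypersensitivity (including anaphylactic reactions and anaphylactic shock" (closing bracket omitted), and Appendix 4 registers anaphylactic reactions. On the documents' own vocabulary the word could be read to cover a registered SAR. This overlap is weaker than the renal one, because the surrounding list concerns conditions described as not serious.

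7. **Size.** An expected count needs a frequency. Interstitial nephritis has none in Appendix 2 or in the product summary, so no count can be derived for it.

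**The case against.** The best defence is that Appendix 6 is commentary, not an operative rule. The daily form, the outcome and section 8.3 all send the reader to Appendix 4, and the SAR list in Appendix 4 ends by referring to Appendix 6 for whatever is not registered. On that reading Appendix 6 explains why other reactions were left off the list and cannot cancel an item that is on it. This stands as far as the consequence goes: the documents do not support saying that nephritis *will* be omitted or that the SAR count *is* too low. It does not dispose of the conflict, because Appendix 6 is worded as an instruction and covers the registered reaction by class.

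Three further limits stand.

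- **The SAP.** Its secondary outcome 6 takes the SAR definition from the SAP's own appendix 2, which is not part of the combined document. Whether that appendix resolves the overlap cannot be checked.
- **Anaphylaxis.** A reader might infer that it is excluded in the same way. The documents do not support putting the two on a par. In Appendix 6 the word stands beside rash and pruritus, while Appendix 4 requires urticaria plus a circulatory or airway feature or bronchodilator treatment. The natural reading is that only mild hypersensitivity goes unregistered.
- **Size.** A reader might infer that one missed case would change the statistical result for SARs. The plan gives no expected SAR count, so any split between arms would be invented. The rare band attached to hypersensitivity gives 1675 × 1/10,000 = 0.17 to 1675 × 1/1,000 = 1.7 cases in the pantoprazole arm. That range belongs to hypersensitivity and cannot be carried over to nephritis.

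**Conclusion.** The point holds in a narrow form. Appendix 6 and Appendix 4 contradict each other on the registration of biopsy-confirmed interstitial nephritis, and nothing in the protocol says expressly which governs. A site following Appendix 6 could omit a case, and the SAR count could be too low by that case. A site giving Appendix 4 priority would record it.

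The effect cannot be quantified, and the primary outcome is not affected. The conclusion assumes that Appendix 6 means the class named in Appendix 2 and the product summary, and that the SAP's SAR appendix does not already settle the matter. This is a minor inconsistency of wording, not a fault in the choice of safety outcomes. It is worth correcting because it lies in a safety definition with little backstop.

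**What to change.** Reconcile the two appendices with two changes of wording.

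- In Appendix 6, replace the renal sentence with: *Renal and urinary disorders other than interstitial nephritis as defined in Appendix 4 will not be registered.*
- In section 8.3, add: *Any reaction meeting an Appendix 4 SAR definition is always registered, whatever Appendix 6 says of its class.* This also settles the weaker ambiguity about hypersensitivity and anaphylactic reactions.

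Send sites a short clarifying note, and confirm that the SAP's SAR appendix agrees. The cost is two sentences and one note. No new data field and no change to the analysis is needed.
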